10.4.5 SAFETY ANALYSIS

The safety analysis will be done by analyzing spontaneous reports of adverse events (AE), subjects' completed 10 cm discomfort/pain visual pain scale and a response questionnaire as well as analysis of immediate response reports by the principal investigator from his/her observation/examination of the treated area. Appropriate Medical Dictionary for Regulatory Activities (MedDRA) code will be used to describe all spontaneously reported or other study related adverse events.

Summaries of spontaneously reported or other study related adverse events will be presented as:

- Number (%) of subjects with any AE,
- Number (%) of subjects with any serious adverse events (SAE),
- Number (%) of subjects permanently withdrawn from treatment due to AE

Summaries of analysis of immediate response reports by the principal investigator examination will be displayed on a bar or pie chart as;

- the overall frequency of subjects with each event (pain during treatment, hemorrhage, burn, erythema, edema, purpura)
- Frequency of subjects with specific severity/intensity for each event using a 5 points scale: 1=none; 2=trace; 3=moderate; 4=marked; 5=severe
- The overall percentage or proportion of subject observed with marked or severe intensity of any event will be calculated and compared to those with none, trace or moderate severity/intensity with the aid of a bar or pie chart.

The following will be considered for the analysis of 10 cm discomfort/pain visual pain scale scores safety data:

A summary table of the 10 cm discomfort/pain visual pain scale scores post treatment will be displayed as mean difference, standard deviation and standard error. The 10 cm discomfort/pain visual pain scale is a 11-level (0 to 10) ordinal scale tool for assessing pain.

The overall percentage or proportion of subject that recorded marked or severe post treatment discomfort/pain visual pain scale scores may be calculated and compared to those with none, trace, low or moderate discomfort/pain using a bar or pie chart.

10.4.6 ADHERENCE AND RETENTION ANALYSES

Adherence to the protocol will be assessed by calculating the number or (%) subjects' data for each endpoint assessment that is not provided in subjects Case Report Forms. This will be further analyzed as per frequency of each endpoint data that is not available due to loss to follow-up, discontinuation of the intervention or any other reason.

10.4.7 BASELINE DESCRIPTIVE STATISTICS

Subjects baseline measurements and scores of all applicable endpoints will be compared using descriptive statistics such as mean score, standard deviation, standard error, range and graphical presentations.

10.4.8 PLANNED INTERIM ANALYSES

No interim analysis is planned.

10.4.8.1 SAFETY REVIEW

There will be no interim analysis during this study. However, this study may be temporarily suspended or prematurely terminated if there is sufficient reasonable cause as per section 5.5 and 8.5.

10.4.8.2 EFFICACY REVIEW

There will be no interim analysis during this study. However, this study may be temporarily suspended or prematurely terminated if there is sufficient reasonable cause as per section 5.5 and 8.5.

10.4.9 ADDITIONAL SUB-GROUP ANALYSES

Not applicable. Primary or secondary endpoints may be analyzed based on age, sex, race/ethnicity or other demographic characteristic(s).

10.4.10 MULTIPLE COMPARISON/ MULTIPLICITY

Not applicable.

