10.2 STATISTICAL HYPOTHESES

The null and alternative hypotheses for the study's primary, key secondary and safety endpoints are;

- Primary Efficacy Endpoints: Statistical hypothesis will not be applied in the analysis of the study's primary endpoint
- Secondary Efficacy Endpoint(s):
 - Null Hypothesis ($H_0: \mu_d = \mu_{post} - \mu_{baseline} = 0$) – There is no change in thickness of the adipose layer as measured by ultrasound (US) at twelve weeks post-treatment as compared to baseline.

Alternative Hypothesis ($H_a: \mu_d = \mu_{post} - \mu_{baseline} \neq 0$) – There is a change in thickness of the adipose layer as measured by ultrasound (US) at twelve weeks post-treatment as compared to baseline. The efficacy endpoint to treatment will be defined by reduction in abdominal fat determined by decrease in thickness of the adipose layer as measured by ultrasound (US) at twelve weeks post-treatment as compared to baseline.

- Null Hypothesis ($H_0: \mu_d = \mu_{post} - \mu_{baseline} = 0$) – There is no change in abdominal circumference at twelve weeks post-treatment as compared to baseline.

Alternative Hypothesis ($H_a: \mu_d = \mu_{post} - \mu_{baseline} \neq 0$) – There is a change in abdominal circumference at twelve weeks post-treatment as compared to baseline. The change will

be defined by reduction in abdominal circumference at twelve weeks post-treatment as compared to baseline.

- Null Hypothesis ($H_0: \mu_d = \mu_{post} - \mu_{pre} = 0$) – There is no satisfaction with the treatment at twelve weeks using the 5-Point Likert Subject Satisfaction Scale as assessed by the subjects.

Alternative Hypothesis ($H_a: \mu_d = \mu_{post} - \mu_{pre} \neq 0$) – There is satisfaction with the treatment at twelve weeks using the 5-Point Likert Subject Satisfaction Scale as assessed by the subjects.

- Safety Endpoint: Statistical hypothesis will not be used in the analysis of the study's safety endpoint.

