10.4 DESCRIPTION OF STATISTICAL METHODS

10.4.1 GENERAL APPROACH

This is an open-label, baseline-controlled, evaluator-blind multi-center study evaluating one treatment with a 1060 nm diode laser for non-invasive fat reduction of the abdomen.

All summary tables for quantitative parameters will display mean, standard deviation, median, range (minimum and maximum), percentages as well as number of missing data (if relevant). All summary tables for qualitative parameters will display counts, percentages and number of missing data if relevant. Baseline data are defined as the last photograph and measurement performed before the first treatment on Visit 1.

All statistical tests will be two-sided, where applicable. The level of statistical significance for effectiveness analyses is 5% ($\alpha = 0.05$) for all tests of differences. Where appropriate, t-test and/or two-proportion z-test will be used to compare outcome at twelve weeks post-treatment as compared to baseline. This test will enable us to accept or reject the null hypotheses. Rejection of null hypotheses will establish that:

- The two-sided 95% confidence interval for the difference between the means excludes zero.
- The two means are statistically significantly different at the 5% level ($P < 0.05$) two-sided.

Upon rejection of null hypotheses, further statistical test tools such as Confidence Interval, and/or One-way ANOVA and/or descriptive statistical tools may be used to determine the performance of the treatment.

In order to accommodate imbalances of some baseline of scores or measurements, covariate adjustment analysis may be performed in SAP to estimate adjusted treatment effects for the primary endpoint analysis.

The assumption for the statistical test is that variables are normally distributed within study group and the variation of scores or measurements at twelve weeks post-treatment as compared to baseline is not reliably different.

The safety analysis will be done by analyzing spontaneous reports of adverse events (AE), subjects' completed 10 cm discomfort/pain visual pain scale and immediate response reports by the principal investigator from his/her observation/examination of the treated area. Appropriate Medical Dictionary for Regulatory Activities (MedDRA) code will be used to describe all spontaneously reported or other study related adverse events.

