10.5 SAMPLE SIZE

The change in thickness of the adipose layer as measured by ultrasound (US) at twelve weeks post-treatment as compared to baseline secondary endpoint outcome measures was used to calculate the study sample size.

Sample size calculation using secondary endpoint outcome measure;

- Null and alternate hypotheses:

Null Hypothesis ($H_0: \mu_d = \mu_{post} - \mu_{baseline} = 0$) – There is no change in thickness of the adipose layer as measured by ultrasound (US) at twelve weeks post-treatment as compared to baseline.

Alternative Hypothesis ($H_a: \mu_d = \mu_{post} - \mu_{baseline} \neq 0$) – There is a change in thickness of the adipose layer as measured by ultrasound (US) at twelve weeks post-treatment as compared to baseline. The efficacy endpoint to treatment will be defined by reduction in abdominal fat determined by decrease in thickness of the adipose layer as measured by ultrasound (US) at twelve weeks post-treatment as compared to baseline.

Expected reduction in abdominal fat of 2.65 + 1.41 obtained from a similar study (,Bass LS et al) will be used to determine the sample size.

- In view of the nature of this study in regard to number of visits, we make provision for 10% study drop out, withdrawal or loss to follow-up.
- 2-Tailed Sample Size calculation formula for two Samples was used in the table below:

(1- β), Desired Power	0.8
α , Level of Significance	0.05
μ_d , expected reduction in abdominal fat measured from baseline to 3 month post treatment visit under H_a	2.65
σ , Standard Deviation (obtained from a study)	1.41
$Z_{1-\alpha/2}$	1.96
$Z_{1-\beta}$, (for 80%)	0.84
Estimated Sample Size	40
Estimated Sample Size of each equal group + 10% drop out	44

Conclusion: The estimated sample size for the study and the additional 10% provision for drop out (**44 subjects**) obtained from the secondary endpoint outcome measure calculation is required for this study. However, to ensure statistical significance, up to 50 subjects will be enrolled.

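### Multiplicity is set aside although two testable secondary hypotheses each get two-sided 5% with no order, and a third, on satisfaction, cannot be tested as written

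*Combined protocol and SAP*

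**What the plan says.** - **Multiplicity.** The whole of Section 10.4.10 is "Not applicable".
- **Which endpoints are tested.** Section 10.2 opens by promising hypotheses for the "primary, key secondary and safety endpoints". It then says "Statistical hypothesis will not be applied in the analysis of the study's primary endpoint", and for safety "Statistical hypothesis will not be used in the analysis of the study's safety endpoint". The nulls that remain are all secondary: no change in ultrasound adipose thickness, no change in abdominal circumference, and no satisfaction, the last written as a post-minus-pre mean difference of zero.
- **Level.** Section 10.4.1 states "All statistical tests will be two-sided, where applicable", and also "The level of statistical significance for effectiveness analyses is 5"%, for every test of a difference. Section 10.4.3 repeats this level for the secondary endpoints. Section 10.4.1 adds that the tests lead to accepting or rejecting the nulls.
- **Sizing.** Section 10.5 sizes the trial on the ultrasound endpoint and adds that "to ensure statistical significance, up to 50 subjects will be enrolled".
- **Primary endpoint.** Section 10.4.2 sets a descriptive criterion, an average of 80% of photographs correctly identified.
- **Satisfaction data.** Section 7.3.4 and the schedule of events table place the satisfaction questionnaire at week 12 only.

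**The concern.** A plan that states several null hypotheses, an accept-or-reject rule and 5% for each has a multiplicity question to answer. It can answer by ordering the tests, by dividing the 5%, or by declaring the p-values nominal. This plan does none of these, and no section calls the secondary tests supportive or exploratory.

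What is at stake is the status of a lone significant result. If ultrasound thickness shows no significant change but circumference reaches p < 0.05, nothing in the plan says whether that may be reported as a statistically established reduction. Circumference is the weaker basis for such a claim, since the plan gives it no expected effect, no standard deviation and no power.

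The satisfaction null is a separate fault. It compares a post-treatment mean with a pre-treatment mean that is never collected, so it cannot be tested in that form.

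**Working it through.** **The plan's own figures.** The documents state no familywise error rate, so there is none to reproduce. The nearest stated figure is the sample size of 40 in Section 10.5 (inputs 2.65, SD 1.41, 1.96 and 0.84). It does not reproduce:
- Paired normal formula: (1.41 × 2.80 / 2.65)² = 2.22, so 3 subjects; the exact paired t calculation gives 5.
- The two-sample formula that the section names: 2 × 2.22 = 4.44, so 5 per group.
- The step from 40 to 44 is 40 × 1.1.

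The mismatch is a separate matter, and nothing below depends on how 40 was reached.

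**Step 1: count the testable nulls.** Section 10.2 lists three. Satisfaction has no pre-treatment value, so two remain: ultrasound thickness and circumference.

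**Step 2: chance of at least one two-sided rejection if both nulls are true.**
- Independent tests: 1 − 0.95² = 0.0975, or 9.75%.
- Bound under any dependence: 0.05 + 0.05 = 10%.
- The documents give no correlation between the two measures. Simulation with assumed correlations of 0.3, 0.5, 0.7 and 0.9 gives about 9.5%, 9.1%, 8.4% and 7.0%.

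**Step 3: chance of a false claim of reduction.** Section 10.2 defines efficacy on both measures as a reduction. Under a true null, a two-sided 5% test falls in that direction 2.5% of the time.
- Independent tests: 1 − 0.975² = 0.0494, or about 4.9%.
- Bound under any dependence: 0.025 + 0.025 = 5%.
- Reference for one two-sided 5% test: 2.5%.

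Without an order, the chance of a false claim of benefit is therefore at most double that of a single test.

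**Step 4: power for ultrasound on the plan's inputs.**
- Standardised effect: 2.65 / 1.41 = 1.88.
- Noncentrality at n = 40: 1.88 × √40 = 11.9, against a critical value near 1.96.
- The exact paired t power is already 99.98% with 11 pairs, so at 40 it is above 99.9%.
- Section 10.5 does not say whether 1.41 is the SD of the change. If it were a per-visit SD with zero correlation between visits, the SD of the change would be 1.41 × √2 = 1.99 and the noncentrality about 8.4. Power would still exceed 99.9%.

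**Step 5: what a fixed sequence would do.** Test ultrasound at two-sided 5%, and test circumference at two-sided 5% only after a significant ultrasound reduction. If both nulls are true, any false rejection requires the ultrasound test to reject first, so the familywise rate is at most 5% and a false claim of reduction at most 2.5%. If ultrasound truly falls as the plan assumes, circumference is reached almost always and keeps its full 5%.

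**The case against.** The strongest reply is that the change would seldom alter a decision. If ultrasound truly falls by 1.88 SD, its null is false and cannot yield a false positive; circumference is then the only null at risk, at 5%, with or without a sequence. The 9.75% needs both nulls to be true, contrary to what the plan expects. This stands, and it limits the practical gain to the case where the ultrasound result fails.

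Three stronger readings are tempting, and the documents do not support them.
- **A reader might count three tests and quote 1 − 0.95³ = 14.3%.** The third has no baseline. Section 7.1.1 does place patient-reported questionnaires at visits 1 and 3, but the visit 1 procedures name the lifestyle questionnaire and pain scales, not satisfaction.
- **A reader might infer that the chance of a false claim of efficacy exceeds 5%.** For the two testable endpoints it is at most 5%, because significant increases could not be presented as efficacy. The fair comparison is with 2.5%.
- **A reader might infer that these tests are the trial's only efficacy claims.** They are its only formal hypothesis tests. Section 10.4.2 has the 80% criterion, and no section lets a significant secondary result alone make the trial a success.

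It can also be said that the key secondary label appears only in one lead-in sentence, and that unadjusted secondary p-values are acceptable when declared nominal. Both are fair, but the plan makes no such declaration.

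**Conclusion.** The point holds in a limited form. The entry in Section 10.4.10 does not fit a plan whose only formal tests are several secondary hypotheses, each with its own 5%.

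With the two testable nulls both true, the chance of any two-sided rejection is 9.75% under independence and at most 10%. The chance of a false claim of reduction is about 4.9% and at most 5%, against 2.5% for one test. These figures assume that each test holds its nominal level; positive correlation lowers them. Subgroup analyses, which Section 10.4.9 leaves open, are not counted. Because ultrasound power exceeds 99.9% on the plan's inputs, the exposure arises mainly if ultrasound fails and circumference alone is claimed.

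The missing order is a case for a cheap improvement. The satisfaction null is wrong as written.

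**What to change.** 1. **Section 10.4.10:** replace the entry with a fixed sequence. Ultrasound thickness at twelve weeks is tested first at two-sided 5%. Circumference is tested at two-sided 5% only if ultrasound is significant, in the direction of reduction by which Section 10.2 defines efficacy. Otherwise circumference is reported with its confidence interval and no claim of significance.
2. **Section 10.2:** delete the post-minus-pre satisfaction hypotheses. Report week-12 satisfaction descriptively with a confidence interval, and take satisfaction out of the baseline comparisons in Section 10.4.3.

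**Cost:** a few sentences, which Section 10.1 allows before database lock, and no extra subjects, visits or data. The downside is that circumference cannot be claimed as significant if ultrasound fails, even where the circumference change is real. On the plan's own inputs that loss is very unlikely.

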10.4.11 TABULATION OF INDIVIDUAL RESPONSE DATA

Individual participant data will be listed by measure and time point as appendix to the study report.

10.4.12 EXPLORATORY ANALYSES

Not applicable.

10.5 SAMPLE SIZE

The change in thickness of the adipose layer as measured by ultrasound (US) at twelve weeks post-treatment as compared to baseline secondary endpoint outcome measures was used to calculate the study sample size.

Sample size calculation using secondary endpoint outcome measure;

- Null and alternate hypotheses:

Null Hypothesis ($H_0: \mu_d = \mu_{post} - \mu_{baseline} = 0$) – There is no change in thickness of the adipose layer as measured by ultrasound (US) at twelve weeks post-treatment as compared to baseline.

Alternative Hypothesis ($H_a: \mu_d = \mu_{post} - \mu_{baseline} \neq 0$) – There is a change in thickness of the adipose layer as measured by ultrasound (US) at twelve weeks post-treatment as compared to baseline. The efficacy endpoint to treatment will be defined by reduction in abdominal fat determined by decrease in thickness of the adipose layer as measured by ultrasound (US) at twelve weeks post-treatment as compared to baseline.

Expected reduction in abdominal fat of 2.65 + 1.41 obtained from a similar study (,Bass LS et al) will be used to determine the sample size.

- In view of the nature of this study in regard to number of visits, we make provision for 10% study drop out, withdrawal or loss to follow-up.
- 2-Tailed Sample Size calculation formula for two Samples was used in the table below:

(1- β), Desired Power	0.8
α , Level of Significance	0.05
μ_d , expected reduction in abdominal fat measured from baseline to 3 month post treatment visit under H_a	2.65
σ , Standard Deviation (obtained from a study)	1.41
$Z_{1-\alpha/2}$	1.96
$Z_{1-\beta}$, (for 80%)	0.84
Estimated Sample Size	40
Estimated Sample Size of each equal group + 10% drop out	44

Conclusion: The estimated sample size for the study and the additional 10% provision for drop out (**44 subjects**) obtained from the secondary endpoint outcome measure calculation is required for this study. However, to ensure statistical significance, up to 50 subjects will be enrolled.

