4 STUDY DESIGN AND ENDPOINTS

4.1 DESCRIPTION OF THE STUDY DESIGN

This is an open-label, baseline-controlled, evaluator-blind multi-center study evaluating one treatment with a 1060 nm diode laser for non-invasive fat reduction of the abdomen.

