10.4.2 ANALYSIS OF THE PRIMARY ENDPOINTS

The following will be consider for the analysis primary endpoints:

The results of each Blinded Reviewer's evaluation of photographs taken at three and six moth compared to baseline will be analyzed and the results will be reported as a % of the correctly identified post treatment photographs chosen per Blinded Reviewer. An average of the % of the correctly identified post treatment photographs chosen by Blinded Reviewer will be calculated and used to determine

Bar, pie charts or graphs indicating percentages of the correctly identified post treatment photographs chosen by Blinded Reviewer may also be used to analyse efficacy.

The efficacy endpoint to treatment will be defined by an average of the 80% of the correctly identified post treatment photographs chosen by Blinded Reviewer This will be used to determine if the study meets the primary endpoint expectation.

The % of the correctly identified post treatment photographs chosen by Blinded Reviewer of all subjects who received at least one treatment of Venus Bliss™ and for whom at least one valid post-baseline assessment were obtained will be analysed for these primary endpoints. Mutiple imputation method or modelling of available data may be used for missing data as appropriate.

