10.6 MEASURES TO MINIMIZE BIAS

10.6.1 ENROLLMENT/ RANDOMIZATION/ MASKING PROCEDURES

At screening, once a subject has signed the informed consent, and inclusion/exclusion criteria has been met, a subject number will be assigned. Subjects will receive a unique identifying number that will be composed of a two-digit site number and a three digit subject number in sequence. This unique identifier will be used throughout the entire study and will be entered in the subject's case report form (CRF) and for each treatment. Subjects are not randomized; this is an open-label, baseline-controlled, evaluator-blind multi-center study.

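### Section 10.5: the printed inputs (reduction 2.65, SD 1.41, 80% power, two-sided 5%) require about 5 paired subjects, not 40, and the two-sample formula named neither gives 40 nor fits a one-arm study

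*Combined protocol and SAP*

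**What the plan says.** Section 10.5 (Sample Size) takes the ultrasound change at twelve weeks, a secondary endpoint, as the basis for sizing. Its null hypothesis is that the mean of post minus baseline, mu_d, is zero. The inputs are introduced as "Expected reduction in abdominal fat of 2.65 + 1.41 obtained from a similar study". The table lists power 0.8, alpha 0.05, mu_d 2.65, sigma 1.41, and z values 1.96 and 0.84. The 1.41 is labelled only "Standard Deviation (obtained from a study"). No unit is given, and nothing says whether it is the SD of the change or the SD at one visit.

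The method is stated as "2-Tailed Sample Size calculation formula for two Samples was used in the table below". The result is 40, followed by 44 on a row labelled "Estimated Sample Size of each equal group + 10% drop out". The conclusion treats 44 as the whole study and adds: "However, to ensure statistical significance, up to 50 subjects will be enrolled".

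On design, section 10.6.1 says: "Subjects are not randomized; this is an open-label, baseline-controlled, evaluator-blind multi-center study". Section 4.1 describes a "multi-center study evaluating one treatment with a 1060 nm diode laser for non-invasive fat reduction of the abdomen". Section 10.2 applies no statistical hypothesis to the primary endpoint, so section 10.5 contains the only size calculation in the plan.

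**The concern.** A mean change of 2.65 with an SD of 1.41 is a standardised effect of 2.65/1.41 = 1.88. An effect that large needs only a handful of subjects, so 40 at 80% power looks wrong on sight. The named formula also belongs to a comparison of two independent groups, and this study has none.

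At stake is the justification for enrolment, not the validity of the ultrasound test. The section tells the reader that 40 is what 80% power for 2.65 requires, and that link is the only support offered for treating 40 to 50 people with an investigational device. It also conceals how sensitive the test will be. A statistically significant ultrasound result at this size could come from a change far smaller than the one the sponsor expects.

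**Working it through.** **Inputs (all from the section 10.5 table):** mu_d = 2.65; sigma = 1.41; z = 1.96 and 0.84, sum 2.80; stated result 40; dropout 10%.

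**1. The plan's own figure, by the formula it names.** Two-sample normal formula, per group: 2 × 2.80² × 1.41² / 2.65² = 2 × 7.84 × 1.9881 / 7.0225 = 4.44, so 5 per group and 10 in total. By exact t, 5 per group gives 74.0% power and 6 per group gives 83.4%, so 12 in total. This is not 40. Other routes also fail:
- One-sided testing gives 4 per group.
- Power of 90%, 95% or 99% gives 6, 8 or 11 per group.
- Swapping mean and SD gives 28 paired or 56 per group.
- Putting the difference at 2.65 − 1.41 = 1.24 gives 20.3 per group, or 40.5 in total before rounding and 42 after. This comes close, but the section does not describe it and it contradicts the table's mu_d of 2.65.

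**2. The formula that fits the hypothesis.** Paired normal formula: 7.84 × 1.9881 / 7.0225 = 2.22, so 3 subjects. The normal approximation is poor at this size. Exact paired t power is 43.3% at n = 3, 70.8% at n = 4 and 87.5% at n = 5, so 5 is the usable answer.

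**3. Does the ambiguity in 1.41 matter?** If 1.41 is a per-visit SD, the SD of the change is 1.41 × √(2(1 − ρ)). The correlations ρ below are assumptions; the plan gives none.

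| ρ | SD of change | n, exact paired t |
|---|---|---|
| 0 | 1.99 | 7 (power 83.2%) |
| 0.25 | 1.73 | 6 |
| 0.5 | 1.41 | 5 |
| 0.75 | 1.00 | 4 |
| 0.9 | 0.63 | 3 |

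No row approaches 40. The missing unit has no effect on n, because n depends only on the ratio of 2.65 to 1.41.

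**4. What would make 40 right?** Solving the paired formula for the SD at n = 40: 2.65 × √40 / 2.80 = 5.99 (5.83 by exact t), about four times 1.41.

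**5. What 40 subjects actually deliver.** The noncentrality for 2.65 is 2.65 × √40 / 1.41 = 11.9, or 8.4 with an SD of 1.99. Power exceeds 99.9% in both cases. The change detectable with 80% power (exact t) is:

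| SD of change | n = 40 | n = 44 | n = 50 |
|---|---|---|---|
| 1.41 (as the SD of the change) | 0.64 | 0.61 | 0.57 |
| 1.99 (per-visit SD, ρ = 0) | 0.91 | 0.86 | 0.81 |
| 0.63 (per-visit SD, ρ = 0.9) | 0.29 | 0.27 | 0.25 |

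If the observed SD of the change is 1.41, the smallest observed mean change reaching p < 0.05 at n = 40 is 2.023 × 1.41 / √40 = 0.45, and 0.45 / 2.65 = 17% of the expected reduction.

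**6. Dropout step.** 40 × 1.10 = 44, as the section says. Keeping 40 evaluable after 10% loss needs 40 / 0.9 = 44.4, so 45. The cap of 50 covers both, since 50 × 0.9 = 45.

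**The case against.** The best case against acting is that nothing in the trial's results changes. The test is overpowered rather than underpowered, the endpoint sized is secondary, the primary endpoint carries no hypothesis test, and section 2.2 classes the device as non-significant risk. On that view this is a traceability fault. It is true that no estimate or decision rule is affected. It remains the case that the only sample-size figure in the plan is wrong by about eightfold (40 against 5), and that the section calls 44 subjects required when its inputs do not show it.

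A second objection is that 3 is not a workable answer, since exact power there is only 43%. That is right, and 3 should be printed only as the normal-formula value, with 5 by exact t beside it.

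Third, the two-sample wording may be loose language for baseline and week-12 measurements on the same people, especially as 44 is then used as the whole study. That is possible, and it would make the wording imprecise rather than a conflict of design. The formula would then give 5 or 6 subjects, which still does not explain 40.

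Fourth, 1.41 is most naturally read as the SD of the change, because it sits beside the mean reduction. That is a fair reading, but the plan should say so.

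**Conclusion.** The point holds, and the section is wrong as written. The stated 40 follows from neither the formula named nor the formula that fits: 5 paired subjects by exact t (3 by the normal formula), or 10 to 12 in total for two groups, against 40. The main figure of 5 assumes that 1.41 is the SD of the change. With a per-visit SD and a correlation of zero or above, the need is at most 7. Reference to two samples and equal groups does not fit a non-randomised study with each subject as own control. A larger enrolment raises power; it cannot guarantee a significant result.

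The direction is towards excess, so the ultrasound comparison is not at risk. A size of 40 to 50 may well be reasonable on other grounds, such as safety or precision of the photographic endpoint, but the plan gives no such grounds. This needs correcting because the sample size rests on it.

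**What to change.** In section 10.5:

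1. Replace the calculation with the paired formula and its result: 5 by exact t (3 by the normal approximation), if 1.41 is the SD of the change.
2. State the unit of 2.65 and 1.41, and whether 1.41 is the SD of the change or of a single visit.
3. On that basis, report the power for 2.65 and the change detectable with 80% power at 40 to 50 subjects.
4. Either show the inputs that produce 40 or give the actual reason for 40 to 50. One candidate is the precision of the primary photographic percentage, worked out for the estimator in section 10.4.2: "An average of the % of the correctly identified post treatment photographs chosen by Blinded Reviewer will be calculated".
5. Delete the references to two samples and equal groups, and the claim that enrolling up to 50 secures significance.

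A minor addition: if 40 evaluable subjects are wanted after 10% loss, the figure is 45 rather than 44.

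The cost is one table and some wording. No subjects are added and conduct does not change.
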